8.9 Exploratory Analyses

Analyses of the ICU-free days endpoint will be based on the intent-to-treat principle using imputed data if there is missing outcome data. The mean ICU-free days for the increased protein group will be compared to the mean within the control group using a t-test allowing for unequal variances. The proportion of participants dying before discharge will be summarized by treatment arm and compared using a score-based test for equality of proportions. The time to discharge alive, with death as a competing risk, will be assessed using cumulative incidence functions.

The proportion of participants with trauma who have a diagnosis of pneumonia noted in the trauma registry will be summarized by treatment arm and compared using a score-based test for equality of proportions. To assess the association of transthyretin with VFD, a linear regression analysis will be performed.

The rate of increase in transthyretin will be compared between the two treatment groups using a GEE model to account for the correlation of observations within each study participant. The model will use the identity link and working independence, and covariates for study day, treatment arm, and the interaction of treatment with study day. This exploratory analysis will include all study participants with any transthyretin measures available.

8.10 Safety Analyses

8.10.1 Analyses of Adverse Events

The number and proportion of subjects reporting key adverse events will be summarized for both treatment groups.

For both treatment groups, we will report the average, standard deviation, median, and quartiles of creatinine. The maximum value reported during each of the first four weeks of hospitalization will be summarized (Days 1-7; Days 8-14; Days 15-21; Days 22-28).

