1.6 Study procedures

Screening of all potential subjects will be done by the Registered Dietitian who is assigned to the Critical Care team and is a member of the research team. Potential study subjects will be identified upon admission to the critical care unit and considered for enrollment if they meet inclusion criteria. Once a subject has been identified, we will randomize that subject into one of the two treatment arms. We will randomly assign subjects to receive either additional enteral protein to achieve a total of 2g/kg/day of protein or to standard enteral nutritional support. Due to the limited published information and the variation across hospitals and within our own practice, both treatment groups can be considered standard care. At Harborview, there is no protocol utilizing one method of protein dosing vs the other. Both are approaches used in our critically ill surgical and trauma patients. The University of Washington Institutional Review Board has approved this study with a waiver of documented consent as it is considered minimal risk (.

We will use a **randomized design** to test whether supplementing enteral protein improves patient care and outcomes. Subjects will be followed until discharged from the hospital and clinical data will be obtained from the electronic medical record. The randomization will be done by previously sealed envelopes that contain an equal number of each treatment assignment. Subjects are randomized 1:1 to either no or additional enteral protein.

Standard of care at our institution includes obtaining nutrition-related labs. Vitamin C, Vitamin D, Zinc and other vitamins and micronutrients are typically measured within 24 hours of ICU admission and used to guide supplementation and treat any deficiencies. Circulating transthyretin (TTHY), C-reactive protein (C-RP) are measured approximately weekly in patients requiring greater than 7 – 10 days of nutritional support. Similarly, we often obtain urine for 24-hour total urinary nitrogen (TUN) measurements, and indirect calorimetry (this is a measure, not a lab procedure) after 7 – 10 days of support. Indirect calorimetry is used to adjust caloric intake and to better understand a patient's general use of energy sources. In this trial the dietitian and

clinical team may adjust caloric goals based upon indirect calorimetry. We will not adjust protein intake based upon TUN or TTHY measurements.

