In a subgroup of study subjects, we will also obtain serial blood and urine samples for analyses of metabolites. Each blood sample collected will be 5ml and each urine sample will be 100ml. The samples will be obtained on Day 0 (defined as the day nutritional support is initiated), Day 1 (24 hours later), Day 3 (72 hours later +/- 24 hours), Day 7-13, Day 14-20, Day 21-27, Day 28-34. If the subject is discharged prior to any of these timepoints, we would obtain the final sample on the day of discharge. Only one sample will be collected during the above timepoints.

[figure not shown]
Urine will be collected from the subject's indwelling catheter, if they do not have an indwelling catheter, no urine samples will be obtained. Blood samples will be obtained through an existing IV catheter if possible. If the subject does not have an existing IV catheter, we will obtain the sample by venipuncture by either the bedside RN or the research RN. We have found that without the ability to obtain the samples by venipuncture (with the subject's permission), we are not able to collect the later samples, and this is affecting the data analysis. We will stop all urine collection when the indwelling catheter has been removed. The blood and urine samples will be analyzed for approximately 200 metabolites as well as inflammatory biomarkers.

Patients will be screened, evaluated, and randomized within 96 hours of admission to the ICU by the study dietitian with guidance from the principal investigator in the case of uncertainty whether the patient qualifies. Subjects will be randomized 1:1 to either supplemental enteral protein or standard enteral nutritional support. Randomization is performed using sealed envelopes with the treatment assignment.

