1.13 Description of enteral protein supplementation treatment

The dietitian will calculate energy and protein needs as indicated in *1.11* above. For subjects randomized to the supplemental protein, arm 2 gm/kg/day of Prosource (Medtrition, Lancaster, PA) will be administered via the nasal/oral feeding tube in 60 – 180 ml bolus infusions 2 – 4 times per day, independently of the enteral formula received. That is, the daily target amount of protein will be administered as supplement boluses beginning on the day the patient is enrolled. Once the enteral formula infusion approaches the target rate then the amount of supplemental protein will be gradually decreased. Supplemental protein will be reduced by 50% once the patient received 75% of targeted caloric intake over the previous day (0700 – 0700). Once the patient reaches the target caloric intake for 48 continuous hours, the amount of supplemental protein will be decreased in order that the total protein prescribed equals 2 gm/kg/day.

2 Data safety monitoring plan

Safety of our intervention will be reviewed by an independent Data Safety Monitoring Board (DSMB) after at 2 timepoints during the trial. The committee will include surgical intensivists who also have experience with clinical and translational research. Data for review will be

prepared by the study analyst ([name]) and study biostatistician ([name]). The review will be iterative. After review of the summary information, additional data from the EMR can be added at the request of the members. Members will also have access to individual patient/study subject records as needed for additional details.

3 Modifications to the study from initial protocol

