Intercurrent events: Subjects may be missing transthyretin due to death, discharge from the hospital, or recovery. Those participants who die will have a transthyretin level equal to the lowest value observed amongst the surviving subjects. Participants who are discharged alive

from the hospital before the primary outcome is measured will have a transthyretin level set equal to the highest observed measure. Multiple imputation will be used to account for study participants who did not have transthyretin measured in the expected window.

Summary measure: The difference in mean transthyretin levels between treatment arms.

5. Study Population

The investigation will enroll 500 subjects using the following inclusion and exclusion criteria:

Inclusion: critically ill adult trauma patients who are started on enteral nutrition within 72 hours of admission to the intensive care unit and are expected to require nutritional support for at least 1 week. Non-trauma post-surgical patients meeting study entry criteria will be included as well. This is expected to include patients recovering from emergency surgery, including amputations, debridement of necrotizing soft-tissue infections, and other serious surgical illnesses.

Exclusion: An individual who meets *any* of the following criteria will be excluded from participation in this study:

- Significant chronic organ failure,
- severe malnutrition,
- not expected to survive due to severity of injuries and,
- serum creatinine >2 mg/dl.

6. Data sources

Data will be collected concurrently with study subject enrollment and treatment in the intensive care unit. extracted from the electronic medical record.

7. Outcomes

7.1 Primary endpoint:

Circulating transthyretin concentrations measured 14 – 21 days after injury.

7.2 Secondary endpoint:

- Ventilator free days: the numbers of days on which the subject does not require assisted ventilation during the first 28 days following the date of injury. VFD will be set to zero for all participants who die before hospital discharge.
- Hospital acquired pneumonia: Pneumonia diagnosed while the patient is in the hospital. Pneumonia will be defined as the presence of a positive quantitative culture from a bronchoalveolar lavage sample coupled with the use of antibiotics.

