8.10.2 Other Safety Analyses

The number and proportion of subjects receiving dialysis during their hospitalization will be summarized for both treatment groups.

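### Weekly maximum creatinine is counted from hospitalization, with no rule for dialysis or departure from hospital, which can dilute the renal comparison between arms

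*SAP*

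**What the plan says.** For each arm, SAP 8.10.1 states that "we will report the average, standard deviation, median, and quartiles of creatinine". It then sets the windows: "The maximum value reported during each of the first four weeks of hospitalization will be summarized", labelled Days 1-7, 8-14, 15-21 and 22-28. The clock named is the hospital stay. The section gives no baseline value, change from baseline, event threshold or number contributing per window. It has no rule for creatinine measured after dialysis begins.

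SAP 8.10.2 treats dialysis as a separate count: "The number and proportion of subjects receiving dialysis during their hospitalization will be summarized for both treatment groups". Nothing combines the two. SAP 8.11 promises confidence intervals for safety analyses, but 8.10 names no renal contrast between arms to which an interval would attach.

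Three other provisions bear on this:

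- **Timing of exposure.** Protocol 1.6: "Patients will be screened, evaluated, and randomized within 96 hours of admission to the ICU". Protocol 1.13 starts the supplement boluses "beginning on the day the patient is enrolled".
- **Entry creatinine.** SAP section 5 excludes patients with "serum creatinine >2 mg/dl", so values up to 2 mg/dl may enter.
- **End of observation.** Protocol 1.6: "Subjects will be followed until discharged from the hospital". Protocol 1.10 confines outcome data to the index hospitalization. SAP section 4 foresees transthyretin values lost to death, discharge or recovery and says how to treat them. Creatinine has no counterpart, and SAP 8.12 limits multiple imputation to the primary and secondary analyses.

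**The concern.** The intervention is a protein load, and three of the four entries among the safety outcomes in SAP 7.6 are renal (dialysis, blood urea nitrogen, creatinine). The creatinine table is the only planned analysis that could show renal injury short of dialysis. Three features make it less sensitive than it need be.

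1. **Clock.** A maximum keeps the highest value in its window. If the highest value in Days 1-7 is an early peak from before randomization, that patient's entry says nothing about the supplement.
2. **Dialysis.** Dialysis removes creatinine. In windows after it starts, the patients with the worst renal course can contribute lowered values.
3. **Shrinking groups.** Weeks 2 to 4 describe patients still in hospital. Death and discharge come after randomization and are themselves trial outcomes, so treatment could affect who remains.

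In a safety comparison, dilution errs towards reassurance.

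**Working it through.** **Plan's own figure.** There is none. The documents give no rate or expected value for creatinine, dialysis or renal injury. Their only design calculation concerns transthyretin and is not an input here.

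**Step 1: pre-randomization share of Days 1-7.** The limit in Protocol 1.6 is 96 h, and 96/24 = 4 days. Assume that ICU admission is hospital day 1. Randomization at 24, 48, 72 or 96 hours then puts 1/7, 2/7, 3/7 or 4/7 of the window (14%, 29%, 43%, 57%) before assignment. If ICU admission comes later in the stay, the share is larger. The documents give neither the usual time to randomization nor the gap between hospital and ICU admission.

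**Step 2: direction.** Let A be a patient's highest value before randomization and B the highest after it, within the window. The table uses max(A, B). A has the same distribution in both arms by randomization. If treatment raises B by d, max(A, B) rises by something between 0 and d. The effect is dilution and extra noise, not a false difference.

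**Step 3: illustration.** Every input is an assumption: 300 simulated trials of 250 per arm; kidney injury in 8% v 14%; mean rise 2 mg/dl; onset on days 5 to 14; randomization on day 4; an early transient rise in both arms alike; 85%, 65% and 45% still in hospital in weeks 2, 3 and 4, independent of arm and renal status; 0%, 25% or 50% of injury cases dialysed four days after onset, with values capped at 1.5 mg/dl from then. SE is the spread of the arm difference across simulated trials.

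Week 1, difference in mean maximum (mg/dl):

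- Post-randomization days only: 0.019, SE 0.029; ratio 0.019/0.029 = 0.66.
- SAP window: 0.012, SE 0.052; ratio 0.012/0.052 = 0.23.

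The fall of 0.007 is modest against simulation error (0.052/√300 = 0.003). The wider SE is the clearer effect.

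Later weeks, difference in mean maximum (mg/dl), with the reduction relative to no dialysis:

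| Window | None dialysed | 25% of cases dialysed | 50% of cases dialysed |
|---|---|---|---|
| Days 8-14 | 0.102 | 0.102 | 0.102 |
| Days 15-21 | 0.118 | 0.104 (12%) | 0.088 (25%) |
| Days 22-28 | 0.118 | 0.097 (18%) | 0.077 (35%) |

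Week 2 does not move because, with these timings, each case that is dialysed by day 14 reaches its peak in that window before dialysis. The SE also falls when high values are capped, so the ratio of difference to SE drops less: in week 3 from 0.118/0.086 = 1.37 to 0.088/0.072 = 1.22 (11%), and in week 4 from 0.118/0.098 = 1.20 to 0.077/0.074 = 1.04 (14%), both at 50% dialysed.

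Mean numbers contributing per arm were 250, 212, 162 and 112. Departure was independent of arm, so this shows loss of information and says nothing about selection.

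**Step 4: does the dialysis count make up for it?** With 25% or 50% of cases dialysed, the rates are 0.25 × 8% = 2.0% v 0.25 × 14% = 3.5%, or 4% v 7%. With 250 per arm and a two-sided 5% test, power is 17% and 31%. At the underlying 8% v 14% it would be 57%, if an event measure captured every case.

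**The case against.** The case against is substantial. Dialysis is reported by arm, death before discharge is compared by arm, and time to discharge alive is assessed with death as a competing risk (SAP 8.9). Harm severe enough for dialysis, and unequal attrition, would therefore show elsewhere. The 96 hours is a limit, not a typical delay. The weekly maximum often keeps the peak in the week dialysis starts. The table is descriptive and drives no primary or secondary conclusion. All of that stands.

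What it leaves open is injury short of dialysis, where the dialysis count has few events and blood urea nitrogen has no analysis described in 8.10. Medians and quartiles do not help: an event in 5% to 15% of patients barely moves them, with or without dialysis.

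Two stronger readings are tempting.

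- **A reader might infer that the plan hides renal harm.** The documents do not support this, given the separate reporting of dialysis and death and the result of Step 2.
- **A reader might put the loss at more than half.** Take dialysis in 5% v 8%, creatinine of 6 mg/dl if not dialysed, 3 on dialysis and 0.8 in everyone else. The arm difference falls from 0.03 × 5.2 = 0.156 to 0.03 × 2.2 = 0.066, or 58%. None of those inputs is in the documents, and the sum treats each dialysed patient's weekly maximum as an on-dialysis value, which a maximum often avoids. The undialysed value it compares with is also unobservable.

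**Conclusion.** The point holds as a cheap improvement to safety reporting. From the text alone, the first window can contain pre-randomization values, on up to about 4 of its 7 days if ICU admission is hospital day 1. The later windows can contain values lowered by dialysis and are confined to patients still in hospital, with no number contributing specified. This can dilute the creatinine comparison; the documents do not show that it does.

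The size cannot be computed. The 12% to 35% reduction in weeks 3 and 4 rests wholly on the assumptions in Step 3 and is smaller relative to the SE. Whether the shrinking groups add selection bias, and in which direction, depends on whether death and discharge differ by arm. The efficacy analyses are unaffected.

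**What to change.** In SAP 8.10:

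1. Count the four windows from randomization. Report the last pre-randomization creatinine by arm and the number contributing per arm in each window.
2. Add one renal event measure for all randomized patients: dialysis, or a stated rise in creatinine from the last pre-randomization value (doubling, for example), by day 28 or discharge. Give the risk difference with a 95% CI. Write the threshold down before the renal data are tabulated by arm.
3. Report death alongside as a competing event, so that patients who die early do not pass simply as free of the event.
4. Keep dialysed patients in the weekly table and flag them, with a sensitivity version that carries forward their highest pre-dialysis value. Do not drop their values: in the simple example under the objection, everyone left would be at 0.8 mg/dl and the arm difference would go from 0.066 to 0.

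The cost is one derived safety variable and some programming. A pre-randomization creatinine should exist, since the entry criterion needs one. The SAP specifies only whether dialysis occurred, so the start date must come from the medical record, for the sensitivity version and to place dialysis before or after day 28.

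The measure should be labelled post hoc. Protocol 3.4 describes differences between arms in respiratory adverse events seen after initial analyses, with the resulting chart review finished on 1 April 2023. The SAP is dated 20 August 2023. Whether renal data had been seen by arm is not stated.

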8.10.2 Other Safety Analyses

The number and proportion of subjects receiving dialysis during their hospitalization will be summarized for both treatment groups.

8.11 Multiplicity

In this study we will use an alpha level of 0.05 for the primary and secondary comparisons. For exploratory and safety analyses, confidence intervals but not p-values will be provided.

8.12 Missing Data and Sensitivity Analyses

The primary and secondary analyses will be performed by multiple imputations to alleviate, as much as possible, the impact of any missing data (death, loss to follow-up, or participant withdrawals) on the analysis of those outcomes. Estimates across the 20 imputations will be combined using Rubin's approach (Rubin 1989). Additionally, sensitivity analyses will be performed using a tipping point analysis. The tipping point analysis will investigate how extreme the values of the missing data must be to change the conclusions of the trial (if that is possible).

8.12.1 Multiple Imputation

Twenty complete imputed datasets will be created using linear regression. The multiple imputation model will be performed within each treatment group for those who survive hospital discharge, and within deaths separately. Covariates will include age, sex, race/ethnicity, NUTRIC score, ventilator free days, and previous values of transthyretin when available. For each complete dataset, the differences in means between treatment groups as well as the standard error of that difference will be calculated; these results will be combined across imputations using Rubin's rule.²

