8.6 Primary Analysis

A t-test with unequal variances will be used to test the primary hypothesis. The analysis will use 20 imputed data sets, with results combined across imputations.

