8.8 Subgroup Analyses

The primary analysis will be repeated in subgroups defined by:

- mNUTRIC score (<5 vs ≥ 5),
- CRP (> 100 vs ≤ 100),
- CRP (> 100 vs ≤ 100) at day 14 (+/-) in those participants in the ICU at least 7 days; and,
- Trauma patients only.

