With 500 participants this study has 80% power to detect a difference of 2.4 mg/dl in average circulating transthyretin levels during the third week between the protein supplementation group (assumed average circulating transthyretin level of 14.4, and the standard of care group (assumed average circulating transthyretin level of 12.0, with a pooled standard deviation of 7.0). This conservatively assumes that there will be 25% of the patients for whom the protein supplementation has no effect in that they are either well enough to have high circulating transthyretin levels or die prior to obtaining the primary outcome. Because the primary outcome is a surrogate marker, we do not plan for any formal interim analyses to evaluate efficacy or futility. Safety of our intervention will be reviewed by an independent Data Safety Monitoring Board (DSMB) on a regular basis. Currently, the Harborview Medical Center typically admits about 300 - 350 trauma victims per year who would meet eligibility criteria. With enrollment over 4 - 5 years, we anticipate that ~1500 patients will be eligible. Therefore, the rate of recruitment among eligible patients needs to be ~33%. The statistical analysis of the primary hypothesis will use a two-sided t-test with alpha of 0.05. We expect that less than 10% of patients will die prior to day 21. For these and for patients who are lost-to-follow-up prior to day 21, we will multiply impute the primary outcome separately for each group and incorporate previously observed circulating transthyretin levels (if available) and patient age information as well as sex, race/ethnicity, NUTRIC score, and ventilator free days.

10. Statistical and Data Programming

All data cleaning and programming will be done in either the statistical software R (R Foundation) or in SAS (SAS).

References (for this document: Statistical Design and Power)

2. Rubin DB. *Multiple imputation for nonresponse in surveys*. Wiley series in probability and mathematical statistics Applied probability and statistics,. Wiley; 1987:xxix, 258 pages.

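### The imputation model omits CRP and trauma status, so if the treatment effect truly differs by CRP, the planned CRP-subgroup estimates are pulled toward the common effect

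*SAP*

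**What the plan says.** SAP 8.6 compares mean transthyretin between arms with an unequal-variance t-test on multiply imputed data: "The analysis will use 20 imputed data sets, with results combined across imputations". SAP 8.8 then states: "The primary analysis will be repeated in subgroups defined by" mNUTRIC (cut at 5), CRP (cut at 100), CRP around day 14 among patients with an ICU stay of seven days or more, and trauma patients alone. SAP 7.3 prespecifies the same four.

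SAP 8.12.1 creates the 20 data sets by linear regression, run by arm for patients who leave hospital alive and separately for deaths. The predictors are given as: "Covariates will include age, sex, race/ethnicity, NUTRIC score, ventilator free days, and previous values of transthyretin when available". SAP section 9 gives the same list, and Protocol 1.7 names only earlier transthyretin and age. NUTRIC is in the SAP model. CRP and trauma status are in none of the lists, and no text says that imputation is rerun inside a subgroup.

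SAP section 4 limits who reaches the regression. Deaths take the lowest value seen in survivors, patients who went home alive before measurement take the highest observed value, and multiple imputation covers those not measured in the window. Neither document gives the expected share of imputed patients.

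**The concern.** An imputation model should contain the variables on which the later analysis conditions. Here, within an arm, a missing value has the same expected value for a high-CRP and a low-CRP patient whose listed covariates agree. Imputed patients therefore bring the arm's average effect into both CRP strata, and a real difference between the strata is diluted.

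What is at stake is the answer to whether inflammation modifies the effect of protein on transthyretin. Protocol 1.11 reports subgroups by confidence interval only, so the affected estimates and intervals are all the reader will see. The tipping-point analysis in SAP 8.12.2 would not reveal the problem, because it applies one shift to all missing values in the treatment arm regardless of CRP.

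**Working it through.** **Inputs from the SAP.** 500 patients at 1:1, so 250 per arm; difference 2.4 mg/dl; SD 7.0; two-sided alpha 0.05; 25% of patients with no effect (section 9). Twenty linear-regression imputations within arm (8.12.1).

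**The plan's own figure.** Diluted difference = 0.75 × 2.4 = 1.8. Standard error = 7 × √(2/250) = 0.626. Power = Φ(1.8/0.626 − 1.96) = Φ(0.915) = 0.820 (0.818 by noncentral t). This agrees with the stated 80%. The point below takes only the sample size, SD and overall effect from it.

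**Assumptions, not in the documents.** CRP splits patients 50/50. True effects are 0 (high CRP) and 4.8 mg/dl (low CRP), averaging 2.4. High CRP lowers transthyretin by 3 mg/dl in both arms. The imputed share f is 10%, 25% or 40%, missing at random with no dependence on any variable. The imputation model holds one earlier transthyretin value; the other listed covariates and the rule-assigned values were not simulated.

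**Formula when earlier transthyretin carries none of the CRP difference.** Stratum estimate = (1 − f) × stratum effect + f × overall effect, so gap = 4.8 × (1 − f).
- f = 25%: 0.25 × 2.4 = 0.6, and 0.75 × 4.8 + 0.6 = 4.2; gap 3.6.
- f = 40%: 0.96 and 3.84; gap 2.88.

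**Simulation** (400 trials per setting, 20 imputations, CRP omitted). Entries are the estimated gap, with the loss (4.8 − gap)/4.8 in brackets. The first column spans correlations of 0 and 0.6 between the earlier and third-week values. The other two use 0.6, with the earlier value carrying the CRP main effect and half or all of the treatment effect.

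| Imputed | Carries none | Carries half | Carries all |
|---|---|---|---|
| 10% | 4.22–4.41 (8–12%) | 4.59 (4%) | 4.65 (3%) |
| 25% | 3.50–3.69 (23–27%) | 4.04 (16%) | 4.45 (7%) |
| 40% | 2.82–2.86 (40–41%) | 3.73 (22%) | 4.32 (10%) |

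Each stratum mean has a simulation error of about 0.05, so a gap has about √(0.05² + 0.05²) = 0.07.

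**Checks.**
- With CRP in the within-arm model, or with imputation within arm by CRP stratum, the gap at 25% imputed is 4.68–4.88, which is 4.8 within simulation error.
- With CRP omitted, the overall effect stays at 2.35–2.45 in every setting.
- With true effects of 2.4 in both strata, the estimates are 2.44 and 2.33: no bias beyond simulation error.

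**Trauma patients alone.** Assume effects of 2.4 in trauma and 0 in non-trauma patients, with 25% imputed. At an 80% trauma share the overall effect is 1.92, and the formula gives 0.75 × 2.4 + 0.25 × 1.92 = 2.28. The simulation gave 2.30 with trauma status omitted and 2.45 with it included. At a 90% share it gave 2.31 and 2.34, which cannot be told apart.

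**Scale.** With 125 per arm in a stratum and no missing data, the 95% half-width is 1.96 × 7 × √(2/125) = 1.7 mg/dl. At 25% imputed with nothing carried, the high-CRP estimate is 0.59–0.68 instead of 0, a shift of a little over a third of that half-width.

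**The case against.** The other side has several sound points.

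- **Wording.** The covariate list does not claim to be exhaustive, and repeating the primary analysis could mean re-imputing within each subgroup, which would remove the problem. That reading is possible. But SAP 8.12.1 describes one set of 20 data sets, stratified by arm and survival only, and nothing mentions re-imputation. If it is intended, the SAP should say so.
- **Who is imputed.** Values set by rule in SAP section 4 do not shrink, and nothing supports a share as high as 40%. This stands. SAP 8.12, 8.12.1 and 9 also describe imputing deaths, which would raise the share; that conflict is a separate matter.
- **Earlier transthyretin.** It is in the model and is measured about weekly during longer support (Protocol 1.6), so it may carry much of the difference. This stands, and it is why the loss is given as a range.
- **Consequence.** No interaction test or between-stratum contrast is planned, and the intervals are wide. This limits the harm, but readers will still compare the two CRP estimates.

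Two stronger readings are tempting. A reader might infer that trauma and non-trauma effects are pulled together, but only a trauma subgroup is planned, and its estimate moves little if most patients are trauma patients. A reader might also infer that leaving out CRP undermines the missing-at-random assumption for the primary analysis. That would need CRP to predict both missingness and transthyretin beyond the listed covariates. The documents do not show this, and the overall estimate did not move in the simulation, although missingness there did not depend on CRP.

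**Conclusion.** The point holds for the CRP subgroups. As written, the plan understates any true difference in effect by CRP, in a known direction, for values drawn from the regression. For assumed effects of 0 and 4.8 mg/dl the loss is about 7–27% of the gap at 25% imputed and 10–41% at 40%. The upper ends need earlier transthyretin to carry none of the difference. The imputed share, the effects, the CRP split and the correlation are all assumptions, so the actual size is unknown. It is zero if the effect does not differ by CRP.

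For trauma patients alone the shift is slight. Severity is minor to moderate and confined to the subgroup estimates and their confidence intervals.

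**What to change.** In SAP 8.12.1 and section 9, add two items to the within-arm imputation model: the CRP measurements that define the subgroups, and trauma versus non-trauma status. Because imputation is already run by arm, main-effect terms are enough to preserve differences in treatment effect between subgroups. Impute missing CRP jointly with transthyretin by chained equations. State which measurement defines the first CRP subgroup, since SAP 7.3 and 8.8 give it no time. The alternative is to impute within arm by subgroup where numbers allow; the SAP should say which is used. If the main model is already locked, rerun the subgroup analyses with these variables added, as a sensitivity analysis.

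Optionally, use transthyretin measured after day 21 as an auxiliary variable. This is a separate gain in efficiency. Under an assumed AR(1) pattern with week-to-week correlation r, using both neighbours instead of only the earlier one cuts the conditional variance by r²/(1 + r²): 0.25/1.25 = 20% at r = 0.5 and 0.49/1.49 = 33% at r = 0.7. It applies only to patients who missed the window but were measured later, and their number is unknown.

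The cost is a short change of wording and some extra modelling. CRP is measured about weekly in longer-stay patients (Protocol 1.6), and trauma status is needed for the subgroup anyway. The real burden is missing CRP: patients without transthyretin in the window may also lack CRP at that time.
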